3.4 Exclusion Criteria

Prospective subjects who meet any of the following criteria are not eligible for enrollment in this study:

- Implanted electrical medical device, such as a pacemaker, defibrillator, or deep brain stimulator
- Suspected or diagnosed epilepsy or other seizure disorder
- Swollen, infected, inflamed areas, or skin eruptions, open wounds, or cancerous lesions of skin at stimulation site
- Peripheral neuropathy affecting the tested upper extremity
- Presence of any other neurodegenerative disease or dementia. These may include: multisystem atrophy, progressive supranuclear palsy, dementia with Lewy bodies, and Alzheimer's disease.
- Botulinum toxin injection for hand tremor within 6 months prior to study enrollment
- Are participating or have participated in another interventional clinical trial in the last 30 days which may confound the results of this study, unless approved by the Sponsor

A study of safety and efficacy of Transcutaneous Afferent Patterned Stimulation (TAPS) for reduction of action tremor in Parkinson's Disease (PD)	Protocol PD-02
	Rev A; 1-OCT-2020

- Significant caffeine consumption within 8 hours of study enrollment, which may confound the results of the study, where significant caffeine is considered more than 95 mg (equivalent to a cup of coffee).
- Subjects unable to communicate with the investigator and staff
- Any health condition that in the investigator's opinion should preclude participation in this study
- Pregnancy or anticipated pregnancy during the course of the study

3.5 Study Assessments

The following assessments will be done:

Subset of Activities of Daily Living (ADLs)

- Telemedicine, supervised and subject rated
- At home, instructed and subject rated

UPDRS Part III assessment

- Telemedicine, modified Part III (tremor tasks only)

CGI-S, I/PGI-S, I

- *Clinical Global Impression of Severity (CGI-S) & Improvement (CGI-I):* The investigator or designee will rate the subject's overall tremor severity & improvement.
- *Patient Global Impression of Severity (PGI-S) & Improvement (PGI-I):* The subject will self-assess their overall tremor severity & improvement.

Kinematic measurements performed with the Cala Trio device with motion sensors.

3.6 Safety

The safety of the peripheral nerve stimulation will be characterized by the incidence of device and therapy-related adverse events.

For this study, transient skin redness and/or itchiness lasting approximately less than 30 minutes will not be considered an adverse event. Similarly, transient discomfort with stimulation will not be considered an adverse event; however, persistent pain from stimulation will be considered an adverse event. For a complete list of potential risks to the subject see Section 5.2.2.

3.7 Blinding

Subjects and investigators/raters will not be blinded.

3.8 Sample Size

Up to 50 subjects will be enrolled.

A study of safety and efficacy of Transcutaneous Afferent Patterned Stimulation (TAPS) for reduction of action tremor in Parkinson's Disease (PD)	Protocol PD-02
	Rev A; 1-OCT-2020

3.9 Study Design Schematic

[figure not shown]

Figure 2. Study schematic of the study design.

3.10 Subject Recruitment

The study site may use several methods to identify and recruit potential subjects. These methods may include, but are not limited to, evaluation of subjects from their existing clinical practice, referrals from other physicians, review of available databases, or direct subject recruitment via advertising (with prior review and approval from Sponsor and reviewing IRB).

3.11 Pre-Screening/Scheduling

Prospective subjects may be pre-screened for the inclusion/exclusion criteria through an IRB approved script. The subject will be informed that they do not have to answer any questions they would not like to answer. If the subject appears to meet the inclusion/exclusion criteria and chooses to participate, they will be scheduled for a screening visit via telemedicine. Once subject is scheduled for a screening visit, they will be asked to hold their last dose of their Parkinson's medications prior to the visit.

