Overview of Study Visits and Procedures	This study will include both subjects on levodopa and subjects taking other Parkinson's medications/unmedicated for Parkinson's. Subjects will be screened for eligibility and fitted with a Cala Trio device. Due to COVID-19 social distancing requirements, visits requiring physician or subject rated assessments will be conducted via telemedicine (i.e., video call). During Visit 1 (Day -7), enrollment will consist of subject eligibility/screening using clinician rated UPDRS assessments. During Visit 2a (Day -1), subjects will receive device training and calibration instructions. During Visit 2b (Day 0), UPDRS assessments and ability to conduct ADLs will be assessed pre and post stimulation session. Visits 2a and 2b may be combined into a single visit. Subjects will use Cala Trio at home for a period of 4 weeks (Day 1- Day 28). During Visit 3 (Day 28), the subjects will exit the study after a UPDRS and ADLs assessment pre and post stimulation session.
Efficacy Assessments	
 • Primary: Within subject comparison of tremor power before stimulation to after stimulation in dominant arm • Secondary: Within subject comparison of ADLs and UPDRS across Visits 1-3
Safety	The safety of the peripheral nerve stimulation will be characterized by the incidence of device and therapy-related adverse events
Number of Subjects	Up to 60 subjects
Number of Sites	1 site
Study Participation	The length of study participation is up to 6 weeks

Subject Population	
Inclusion Criteria	
Prospective subjects must meet all of the following criteria to be eligible for study participation:
 
 • Must be ≥ 22 years of age • Competent and willing to provide written, informed consent to participate in the study • Clinically significant postural tremor as defined by: 
 ◦ Dominant hand/arm exhibiting postural tremor ≥ 2 (while in the off state) as assessed by the MDS-UPDRS postural tremor score • Stable dose of Parkinson's disease medications, if applicable, for 30 days prior to study entry • Willing to comply with study protocol requirements including: 
 ◦ Having the ability to do telemedicine or video calls for study visits ◦ remaining on a stable dosage of Parkinson's medications, if applicable, during the duration of the study ◦ no significant caffeine consumption within 8 hours of study visits

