3.3 Inclusion Criteria

Prospective subjects must meet all of the following criteria to be eligible for study participation:

- Must be ≥ 22 years of age
- Competent and willing to provide written, informed consent to participate in the study
- Clinically significant postural tremor as defined by:
 - Dominant hand/arm exhibiting postural tremor ≥ 2 (while in the off state) as assessed by the MDS-UPDRS postural tremor score
- Stable dose of Parkinson's disease medications, if applicable, for 30 days prior to study entry
- Willing to comply with study protocol requirements including:
 - remaining on a stable dosage of Parkinson's medications, if applicable, during the duration of the study
 - no significant caffeine consumption within 8 hours of study visits
 - Having the ability to do telemedicine or video calls for study visits

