3.12 Informed Consent

When a prospective subject has been identified and prior to beginning protocol-mandated testing, the study will be presented to them for consideration. The subject will be given adequate time to have their questions answered and to carefully consider participation. If, after understanding the purpose, potential risks and benefits, and requirements of the study, as well as their rights as a research subject, the individual agrees to participate, informed consent will be obtained. Informed consent will be documented in the subject's study records.

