3.13 Screening

Following obtaining informed consent, potential subjects will undergo the following evaluations in order to ensure the subjects meet all of the inclusion criteria and none of the exclusion criteria:

- **Document current Parkinson's disease medications and medicine schedule**
- **Tremor Severity:** MDS-UPDRS Part III will be performed.
- **Medical History:** A brief medical history will be conducted to evaluate prior and existing medical conditions that may exclude individuals from the study. No medical records will be used for this study, so all eligibility criteria will be based upon self-

A study of safety and efficacy of Transcutaneous Afferent Patterned Stimulation (TAPS) for reduction of action tremor in Parkinson's Disease (PD)	Protocol PD-02
	Rev A; 1-OCT-2020

reported information from each subject and in-person verification by qualified study staff.

Subjects that don't meet all of the inclusion criteria and meet any one of the exclusion criteria will be considered screen fails.

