3.14 Enrollment

Prospective, eligible subjects are considered officially enrolled in the study after they have signed the informed consent, completed the screening stage, and are confirmed to satisfy all protocol-mandated inclusion and exclusion criteria. If a prospective subject chooses to withdraw during or just after the screening stage but before they begin use of the Cala Trio, they will be considered a screen fail and exited from the study; they will not be counted as enrolled.

3.15 Visit 1

Subjects will be reminded to be in the *off* state, i.e. to skip their last dose of PD medication, prior to their telemedicine Visit 1. The following assessments will occur:

- Screening activities including medication review and medical history. No medical records will be used for this study, so all eligibility criteria will be based upon self-reported information from each subject and verification by qualified study staff.
- Tremor assessments (while in the *off* state) including:
 - Modified MDS Unified Parkinson's Disease Rating Scale Part III (MDS-UPDRS) to confirm eligibility will be rated by the PI
 - Bain & Findley Activities of Daily Living (ADL) upper limb subset score will be rated by the subject based on their recall of the previous week (no props will be used)
- Demographic information, Parkinson's clinical characteristics, and wrist size and handedness will be collected based on self-reported information from subjects.

Once a subject has been confirmed to be eligible for the study, a device kit containing a stimulator, base station and band will be shipped directly to the subject's home ahead of Visit 2.

3.16 Visit 2

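### Protocol 3.11 asks medicated candidates to hold a Parkinson's dose ahead of Visit 1, where Table 1 schedules consent, and no consent rule requires consent before the hold

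*Protocol*

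**What the plan says.** Protocol 3.11 covers pre-screening and scheduling. A person who appears to qualify and "chooses to participate, they will be scheduled for a screening visit via telemedicine". The next instruction is: "Once subject is scheduled for a screening visit, they will be asked to hold their last dose of their" Parkinson's medications before the visit. Section 3.15 repeats it as a reminder to be in the off state, that is, "to skip their last dose of PD medication, prior to their telemedicine Visit 1".

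The purpose is to establish eligibility. Section 3.3 requires a postural tremor score of at least 2 in the dominant hand or arm, rated "while in the off state) as assessed by the MDS-UPDRS postural tremor score". The synopsis places that rating at the first visit: "During Visit 1 (Day -7), enrollment will consist of subject eligibility/screening using clinician rated UPDRS assessments".

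On consent, 3.12 says that once a prospective subject is identified, and "prior to beginning protocol-mandated testing, the study will be presented to them for consideration". Section 3.13 opens with "Following obtaining informed consent, potential subjects will undergo the following evaluations". Table 1 (section 4.0) marks Informed Consent once, in the Visit 1 column.

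**The concern.** The dose hold is a study procedure. The documents give no clinical reason for it; it exists so that tremor can be scored off medication. A change to someone's medication made for research purposes should follow documented consent, after the person has had its risks explained. Here the request comes at scheduling and the dose is skipped before the visit at which consent is scheduled.

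Two features of the plan add to this. First, staff may know little about the person when the request is made. Recruitment may be by advertising, database review or referral (3.10), pre-screening by script is optional (3.11), no medical records are used, and the medication schedule and history are recorded only after consent (3.13). Second, the risks set out in section 5.2 are those of the device and stimulation, so the protocol text does not show that the effect of a missed dose is explained to anyone beforehand.

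What is at stake is the protection of medicated candidates, including those who skip a dose and then fail screening.

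**Working it through.** No arithmetic applies. The check is to put the plan's steps in order and then test each consent rule against the dose hold.

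**Order of steps as written**

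1. The person may be pre-screened with an IRB-approved script (3.11).
2. The person appears eligible, chooses to take part, and is scheduled for the telemedicine screening visit (3.11).
3. Once scheduled, the person is asked to hold the last Parkinson's dose before that visit (3.11).
4. The dose is skipped before Visit 1 (3.15).
5. Visit 1 takes place. Table 1 marks Informed Consent here.
6. The screening evaluations follow consent (3.13).
7. Enrollment follows once candidates have signed consent, "completed the screening stage, and are confirmed to satisfy all protocol-mandated inclusion and exclusion criteria" (3.14).

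Steps 3 and 4 come before step 5, which is the only consent point in the schedule.

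**Each consent rule against the hold**

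- *Section 3.12* ties consent to the start of testing that the protocol mandates. Withholding a dose prepares for a test but is not itself a test. The section neither forbids consent before the hold nor requires it.
- *Section 3.13* places consent before a list of evaluations: the medication record, tremor severity and medical history. The hold is not on the list, and it must already have happened for tremor to be rated in the off state.
- *Section 8.1* names as a deviation the taking of study measurements without written consent. The list is expressly open-ended, but the hold is not among its examples.
- *Section 10.3* has the broadest rule: written consent before any treatment related to the study. In its plain sense this means treatment given; a withheld dose is not named.

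A site could therefore follow each of these sentences and still have a medicated person skip a dose before consent is documented.

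**Consequence for the analysis**

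The device ships only after eligibility is confirmed (3.15). The primary endpoint in SAP 3.3 uses pre- and post-stimulation recordings from therapy sessions, all of which come later. When consent is taken relative to the Visit 1 hold changes none of these data, nor the sample size in Protocol 9.7 and SAP 3.6.

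**The case against.** The strongest reply is that Table 1 cannot bear much weight. Visit 1 is its first column, with none for pre-screening or scheduling, so the mark cannot separate consent taken during the Visit 1 call from consent taken in the days before it. Section 3.12 is the governing text. It starts from the moment a prospective subject is identified, fixes no visit, and requires adequate time and an understanding of what the study demands. For a remote visit with written consent, the form may well arrive before the call. The hold is also a request, made only to people who have chosen to take part. The script and consent form, where instructions about the hold would naturally sit, were not available, and the schematic in Figure 2 was not shown.

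Much of this stands. Consent before the hold is compatible with the protocol, and site practice may already work that way. It does not dispose of the point, because nothing requires that order, and 3.11 read with Table 1 gives the opposite one. Choosing to be scheduled is not the documented consent that 3.12 describes.

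Three stronger readings are tempting, and the documents do not support them:

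- *That the protocol plans to withhold doses without consent.* It is silent on this sequence. It does not direct that consent wait until after the hold.
- *That the start of adverse event collection is contradictory.* Section 6.2 starts at enrollment, and Table 1 marks adverse events at Visit 1. Table 1 also labels Visit 1 as screening and enrollment and confirms eligibility in the same column, so the two agree at visit level.
- *That the share of off-state visits affected measures the size of the problem.* A count of visits is neither a number of people nor a risk. In addition, 3.16.2 requires off-state rating at Visit 2b without an explicit instruction to skip a dose, so even the count of holds is not firm.

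**Conclusion.** The point holds in a limited form. As the protocol is written, a medicated person can skip a Parkinson's dose for the study before documented consent. This is a gap in the written sequence; it is not evidence that any site has worked this way.

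It is small. It concerns the one dose held before Visit 1, for medicated candidates only, and only where consent has not been taken earlier. The documents do not give the number of such people or the risk of one missed dose, so no figure or range is offered. The primary test, the power and the device- and therapy-related safety endpoint are unaffected.

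The conclusion rests on two readings: that treatment in 10.3 means treatment given rather than withheld, and that the unseen script and consent form do not already place documented consent before the hold. If either is wrong, the point reduces to a clarification of wording.

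**What to change.** In 3.11 and 3.12, state that documented remote consent precedes any request to withhold Parkinson's medication. In Table 1, show Informed Consent as at or before Visit 1, with a note that for medicated people it comes before the hold. The medication and schedule record required by 3.13 can be taken at the same contact, so that staff know what is being withheld. The off-state rating and the hold itself stay as they are.

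The cost is wording in two sections and one table, plus an earlier remote consent contact for medicated people. Some of those people will later fail screening, so some consent discussions will be held with people who never enroll. Visits are already by video call, so the change need not add travel.

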3.12 Informed Consent

When a prospective subject has been identified and prior to beginning protocol-mandated testing, the study will be presented to them for consideration. The subject will be given adequate time to have their questions answered and to carefully consider participation. If, after understanding the purpose, potential risks and benefits, and requirements of the study, as well as their rights as a research subject, the individual agrees to participate, informed consent will be obtained. Informed consent will be documented in the subject's study records.

3.13 Screening

Following obtaining informed consent, potential subjects will undergo the following evaluations in order to ensure the subjects meet all of the inclusion criteria and none of the exclusion criteria:

- **Document current Parkinson's disease medications and medicine schedule**
- **Tremor Severity:** MDS-UPDRS Part III will be performed.
- **Medical History:** A brief medical history will be conducted to evaluate prior and existing medical conditions that may exclude individuals from the study. No medical records will be used for this study, so all eligibility criteria will be based upon self-

A study of safety and efficacy of Transcutaneous Afferent Patterned Stimulation (TAPS) for reduction of action tremor in Parkinson's Disease (PD)	Protocol PD-02
	Rev A; 1-OCT-2020

reported information from each subject and in-person verification by qualified study staff.

Subjects that don't meet all of the inclusion criteria and meet any one of the exclusion criteria will be considered screen fails.

3.14 Enrollment

Prospective, eligible subjects are considered officially enrolled in the study after they have signed the informed consent, completed the screening stage, and are confirmed to satisfy all protocol-mandated inclusion and exclusion criteria. If a prospective subject chooses to withdraw during or just after the screening stage but before they begin use of the Cala Trio, they will be considered a screen fail and exited from the study; they will not be counted as enrolled.

3.15 Visit 1

Subjects will be reminded to be in the *off* state, i.e. to skip their last dose of PD medication, prior to their telemedicine Visit 1. The following assessments will occur:

- Screening activities including medication review and medical history. No medical records will be used for this study, so all eligibility criteria will be based upon self-reported information from each subject and verification by qualified study staff.
- Tremor assessments (while in the *off* state) including:
 - Modified MDS Unified Parkinson's Disease Rating Scale Part III (MDS-UPDRS) to confirm eligibility will be rated by the PI
 - Bain & Findley Activities of Daily Living (ADL) upper limb subset score will be rated by the subject based on their recall of the previous week (no props will be used)
- Demographic information, Parkinson's clinical characteristics, and wrist size and handedness will be collected based on self-reported information from subjects.

Once a subject has been confirmed to be eligible for the study, a device kit containing a stimulator, base station and band will be shipped directly to the subject's home ahead of Visit 2.

3.16 Visit 2

3.16.1 Visit 2a

Once a subject has received the device kit, device training will occur via telemedicine, as follows:

3.16.1.1 Positioning and Fastening Cala Trio

Prior to device positioning, subjects should dampen the wrist of the prescribed hand to ensure good connection between the electrodes and wrist. Subjects should position the device on the prescribed hand such that the electrodes are positioned over the median and radial nerves, and securely tighten the band.

A study of safety and efficacy of Transcutaneous Afferent Patterned Stimulation (TAPS) for reduction of action tremor in Parkinson's Disease (PD)	Protocol PD-02
	Rev A; 1-OCT-2020

3.16.1.1.2 *Device Calibration*

To calibrate the Cala Trio device, subjects will perform a series of postural hold tremor tasks, in which the device measures the subject's tremor frequency and sets the stimulation burst frequency based on the measured tremor frequency.

For the purposes of this study, only the outstretched postural hold tremor task will be used.

3.16.1.1.3 *Setting Stimulation Intensity*

The subject will set the stimulation intensity to an amount they can comfortably tolerate while doing light activities. Paresthesia should be perceived in the parts of the hand and/or fingers innervated by the median and radial nerves. The stimulation intensity selected during the initial amplitude calibration is saved on the device for subsequent sessions. The subject can decrease or turn off the stimulation at any point in time, and may adjust their stimulation intensity from session to session to maintain the minimum paresthesia threshold.

3.16.1.1.4 *Device Training*

During the course of the visit, study personnel will instruct the subject on proper use of the device. Subjects must demonstrate competence to operate the device and comprehension of the instructions for use prior to completing the training.

